The FDA has given us advice to try less conservative monitoring guidelines after we initially treat participants in the study and gain more experience. The following will be considered for a modification but only used once amended to the IRB:

1. ANC 1000-1499 /mm³ :monitor weekly for 6 months and then every two weeks for 6 months, then monthly
2. ANC 500-999 /mm³ :hematology consult, continue clozapine, monitor 3x weekly until ≥ 1000/mm³ then weekly for weeks then back to baseline monitoring
3. ANC <500/mm³ :stop clozapine, hematology consult, monitor daily until ≥ 500 /mm³, then 3x weekly until back to baseline, do not rechallenge unless benefit outweighs risk.

In the US [name] from Johns Hopkins University will be the hematologist and consultant hematologist to Nigeria. [name], the Nigerian consultant hematologist from Lagos University Teaching Hospital (LUTH) will be on the protocol in Nigeria. In the case of

severe Neutropenia, one strategy to increase ANC values is to start lithium treatment, however we will not recommend this strategy.

Concomitant Medications:

Subjects may remain on adjunctive anticholinergic, antidepressant, most mood stabilizers and/or anti-anxiety agents. Subjects on such medications are included to increase the generalizability of study results and to relate the study more closely to treatment issues addressed in usual clinical practice. Any medication that may lower WBCs such as carbamazepine will not be permitted to be initiated but treatment for 3 months and consultation with hematologist with treatments that may lower ANC.

Subject Recruitment: Subjects will be recruited from three sites. The MPRC will be coordinating the study. [name], the primary coinvestigator affiliated with MPRC, along with [name] from FNPHY, will oversee study procedures and recruitment from the Nigerian site and [name] will be the primary coinvestigator for the Howard University Site. All sites will have approval by an Institutional Review Board (IRB), however UMB will be the central IRB of record. We plan to enroll at least 250 AA subjects with BEN or past possible BEN (past neutropenia) from the three sites, with approximately 130 subjects from Nigeria (easy to recruit with pure *DARC* +/- population), 120 subjects from the MPRC and 40 subjects from Howard University over a 5 year period. This will be approximately 30 per year from Nigeria, 16 per year from MPRC and 8 per year at Howard University, all fewer than the amount of clozapine starts annually at each site.

A partial HIPAA waiver will be obtained to permit the identification of potential participants through chart review. In addition, participants will be referred by the person's treatment team for consideration of study participation. A chart review will be completed for all potential participants to reduce the likelihood that they will be found ineligible after participating in more extensive assessments. The study recruiter will verify with the primary clinician that a potential participant is sufficiently stabilized to consider participation and has capacity to provide consent. This is done prior to the study recruiter approaching a potential participant. The study recruiter will be introduced to the person and provide a brief overview of the project.

Participants may also be recruited from internet based advertising (HP-00061828) that will refer interested participants to the MPRC web site as well as working with clozapine prescribers from the state of Maryland identified through collaboration with the Behavioral Health Administration and Medicaid.

We will also collect data on WBC, ANC and demographic information on people previously treated in Maryland on a waiver system. Their data is available in clinical charts at Spring Grove Hospital and will only collect with approval from the hospital and the Spring Grove Research Committee. These patients will not be eligible to reenroll in this study but the data will be available to add to the study as it will help decrease the final sample size needed to enroll in the study. We will link this data from another study approval where a waiver of informed consent has been granted to study antipsychotic use (HP-00040084).

PRIMARY OUTCOME VARIABLES:

The primary outcomes are to measure ANC levels, side effects and patient safety.

STATISTICAL ANALYSES:

Analysis of Effect of clozapine on WBC and ANC levels: We will characterize variation of WBC and ANC levels in participants by *DARC* null genotype. We anticipate 212+ AA participants with BEN who are homozygous for the *DARC* null allele who will be the focus of this analysis, with other participants with BEN to be examined in a separate analysis. We will compute within-patient means and standard deviations of weekly WBC and ANC by three months intervals, starting with the three-month pre-treatment phase, and continuing for the six-months of follow-up on clozapine treatment, and observe the frequency of ANC values observed that exceed specific levels of concern (e.g. <500, <700, <1000 cells/mm³). We will estimate the change from baseline in overall average WBC and ANC during each three month interval after initiation of clozapine, and assess whether these change with time using a mixed model for repeated measures ANCOVA, controlling for baseline. Frequency of other events of concern (serious infection, need for treatment for very low ANC) will also be reported. We will also perform analyses of effects of mean participant pre-treatment ANC, clozapine dose and clozapine blood level on mean ANC during clozapine treatment and ANC<500 cells /mm³ during clozapine treatment, using linear and logistic regression. To date all published work and US guidelines are based on non-BEN samples and not specific to schizophrenia patients.

For the study when we report the results we will evaluate a subgroup of people with a history of ANC < 1500 cells/mm³

Risk of Agranulocytosis - Analysis and Power: The analysis of this aim will resemble that for an equivalence trial comparing effectiveness of two treatments, only instead we will be comparing safety outcomes between two populations (patients with and without BEN), using an extremely large historic control group rather than newly recruited controls. We will compare estimated risk of agranulocytosis in our study to a large historic cohort study estimating risk of agranulocytosis in non-BEN patients followed according to current FDA guidelines during clozapine treatment. In a report on 11,555 clozapine-treated patients followed for agranulocytosis. There is an incidence rate of 0.9% at one year (upper 95% CI 0.99), with over 80% of cases observed within the first three months, from which we conclude that our planned six-month follow-up on clozapine is adequate to cover the period of highest risk. Some participants will discontinue clozapine prior to conclusion of the six-month treatment phase. In the CATIE trial, 15% of participants assigned to clozapine had discontinued treatment by six months. To adjust for missing data due to dropout, we will use the Kaplan-Meier method for censored survival data to calculate a point estimate of the proportion of cases of agranulocytosis by six months. However, we anticipate few if any cases of agranulocytosis in our cohort, so that usual methods of calculating a CI for the percent without an event at six months which rely on large sample estimators may not work well. Accordingly, we will also use all clozapine-treated cases, ignoring variation in follow-up on clozapine, to calculate a binomial approximation for an upper 95% confidence limit for the risk, r , of agranulocytosis during the first six-months on by solving the equation $0.95 = 1 - \sum_{j=0}^k \frac{n!}{j!(n-j)!} r^j (1-r)^{n-j}$, where r is probability (risk) of agranulocytosis, n is the total number of participants, k is the number of cases of agranulocytosis, and the summation runs from $j=0$ to k . If no cases are observed, this reduces to $0.05 = (1-r)^n$; we will use similar a similar formula to calculate the lower confidence limit (LCL); if the LCL does not include the risk level in the historic control cohort, we would reject strict equivalence of risk. With $n=212$ *DARC* null homozygous participants, zero cases observed would give an upper limit on the risk of 1.4%, approximately 1.4 x the estimated risk of agranulocytosis in non-BEN patients reported in a U.S. cohort of 11,555 patients treated with clozapine. Thus, we will not be able to demonstrate complete equivalence to the risk of

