The 6-month risk of agranulocytosis in clozapine-treated BEN patients will not differ from reported rates in the literature. In the DARC null allele patients, normal variation in ANCs and WBCs will create sporadic episodes with ANCs below usual U.S. monitoring guidelines ($<1500 \text{ cells/mm}^3$), but not higher rates of agranulocytosis or severe infection. These patients will have lower mean ANC and WBC than patients without the polymorphism, and not have higher rates of agranulocytosis.

Hypothesis 2: (non DARC null allele patients)

BEN patients without the polymorphism will have higher mean ANC than the group with the genetic polymorphism (DARC null alleles), and will be less likely to have episodes with ANCs below usual U.S. monitoring guidelines ($<1500 \text{ cells/mm}^3$). We will evaluate any identifiable causes (e.g., infection) of low ANC in such participants

STUDY PARTICIPANTS:

Inclusion Criteria
Eligible and recommended for clozapine treatment (e.g. treatment resistant schizophrenia, schizoaffective disorder, bipolar disorder, other psychotic disorder, delusional disorder, hostility, other documented rationale)
Male or Female
African Ancestry (African, African-American or African-Caribbean). This population will make up the majority of the study. However, there are cases of BEN in individuals of Middle Eastern, Caucasian, and other ethnicity. We will accept these patients as they may have unknown African ancestry and genotyping will be important. Caucasian subjects will only be recruited if they have a history of an absolute neutrophil count (ANC) $<2500 \text{ cells/mm}^3$ in past 24 months
Age: 18 to 64 years.
Documented ability to sign informed consent. This is a score of $\geq 10/12$ on ESC.
Effective birth control if of child bearing potential

Exclusion Criteria
Pregnancy or lactation
History of myeloproliferative disorder
Uncontrolled seizure disorder
History of paralytic ileus
History of 3 or more successive ANC values below 500 cells/mm^3

Systemic Lupus Erythematosus, Multiple Sclerosis, Hashimoto's Thyroiditis, Sjogren's Syndrome, Grave's Disease*
Medical condition whose pathology or treatment would likely alter the presentation or treatment of schizophrenia or significantly increase the risks associated with the proposed protocol.
Medical condition affecting patient's ability to mount an immune response
Current symptomatic bacterial or viral infection*
Sickle cell anemia
Temperature > 38.0 ° Celsius, 100.4 ° Fahrenheit*

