- All participants will be recommended to undergo 6 weeks of weekly monitoring for ANC and WBC fluctuations and clinical evaluations. This may be fewer if the PI or treatment team feel waiting to begin clozapine would not be in the best interest of the patient. At least one week of observation is needed. This could also go longer if a patient is enrolled and clozapine start is delayed for a short period. After this period, subjects still meeting eligibility criteria will be treated for 6 months with open label clozapine with weekly WBC/ANC

monitoring. We will minimize the burden of assessments to focus on safety and retention and in order to simulate treatment as usual in a naturalistic design.

- Assessments: A full schedule of events is included below. At baseline, all participants will have a standard medical workup including a physical examination, Body Mass Index (BMI) measurement, and EKG (In USA only). Blood will be collected for complete blood count (CBC), Chemistry 14 panel with fasting blood glucose, lipid panel, HIV, thyroid panel, and liver function tests. Additional blood smear analyses for malaria parasites will be performed at FNPHY. A description of the time points for all of the assessments and laboratories are included in the schedule of events.

SCHEDULE OF EVENTS	Visit 1 Screening	Visit 2-5 (Pre-clozapine)	Visit 6 (Week prior to Clozapine start	Visit 7-30
Medical and Psychological evaluation	X			
Demographic information	X			
Inclusion/Exclusion criteria documentation	X			
SCID and DDF form	X			
Smoking status, Fagerstrom Test for Nicotine Dependence (can be done at visit 1 or 2-5)		X		
Blood draw for genotyping (one for storage and one for named genes)	X			
Cytokines (US only)		X		X (2 times) Visit 18 and 30)
Documentation of previous ANCs	X			
Consent and patient monitoring form	X			
HIV testing	X			
Concomitant medication list		X (weekly)	X	X (weekly)
ANC signoff each week		X (weekly)	X	X (weekly)
Blood smear for malarial parasites (Nigerian site)	X	X (every 2 weeks)	X	X (every 2 weeks)
Education/reminder on reporting infection	X	X	X	X (weekly)
Medical record review	X			

CBC with differential	X	X (weekly)	X*	X (visit 7-10 and 30)*
WBC/ANC finger stick**			X	X (weekly) until week 4 then optional thereafter
Chemistry 14 including lipids, liver enzymes, thyroid function, FBG, electrolytes	X		X	X (monthly) Visits 10,14,18,22,26,30)

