Participants enrolled in the study at all 3 sites will receive the modified guidelines (table below) in addition to their informed consent and the investigator and patient will sign the consent acknowledging the modified guidelines. More stringent monitoring may take place if ANC levels fluctuate and modifications from this guideline may occur on a case by case basis with the consultation of a physician, hematologist and PI. During the study subjects will be very closely monitored as per below. Subjects will be educated concerning signs and symptoms of infection and the need to immediately report these throughout the study.

The Food and Drug Administration (FDA) has approved the modified monitoring procedures under an IND:

Absolute Neutrophil Count (ANC) Value	Modified Monitoring Plan Recommendation for Patients with History of or Current Benign Ethnic Neutropenia (BEN). Changes can be made with consultation from hematology. Always consider other medications that may be contributing to ANC suppression.
Clozapine Initiation	
 1. All patients initiating clozapine in the study will have had ANC <2500/mm³ in the past 24 months and those enrolled will not have a history of ANC<500/mm³. 2. Patients with two baseline ANC levels ≥1000/mm³ will be initiated with weekly blood draws. 3. Patients with baseline ANC levels between 500-999/mm³ may be initiated 
 a. After hematology consult and b. With specific oversight plan approved by hematology and study team. c. If initiated, patients will have ANC drawn twice weekly for first month of treatment prior to be considered for weekly monitoring. If ANC levels fall below 500/mm³, treatment will be interrupted as per protocol below. d. Justification for deviation from Risk Evaluation Management System (REMS) recommendations: We recognize that these are more lenient criteria than REMS, however, patients are enrolled in clinical trial with increased monitoring and we will be seeking a hematology consult and oversight prior to initiation and to make a plan for increased monitoring once treatment initiated.
ANC ≥1000/mm ³	Continue weekly ANC monitoring.

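### Two entry rules for a past ANC below 500 give different answers for some patients, and the protocol does not say which governs

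*Combined protocol and SAP*

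**What the plan says.** The Exclusion Criteria under STUDY PARTICIPANTS contain one line on past severe neutropenia: "History of 3 or more successive ANC values below 500 cells/mm^3". Under MONITORING GUIDELINES, item 1 of the Clozapine Initiation row states that "those enrolled will not have a history of ANC<500/mm³".

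The surrounding text bears on how the two fit together:

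- The sentence introducing the table reads "The Food and Drug Administration (FDA) has approved the modified monitoring procedures under an IND". The paragraph before it lets the guideline be modified for individual patients when a physician, a hematologist and the PI are consulted. The table header adds "Changes can be made with consultation from hematology".
- Item 2 of the same row says that patients with two baseline ANCs of at least 1000 "will be initiated with weekly blood draws". Item 3 requires a hematology consult for a baseline of 500-999.
- STUDY DESIGN AND METHODS says that after the observation period "subjects still meeting eligibility criteria will be treated for 6 months with open label clozapine".
- The SCHEDULE OF EVENTS places "Documentation of previous ANCs" at Visit 1.

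Aim 3 defines agranulocytosis as an ANC below 500.

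**The concern.** Two sections state an entry condition on the same measurement at the same cut-off, and they are not the same condition. Three sites must screen against prior counts, and the protocol gives them two answers for anyone with an isolated past value below 500.

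This is a safety criterion set at the level that defines the trial's main safety event. A site that works from the Exclusion Criteria alone could enroll, and then treat, patients whom the initiation table says are not in the study. The binomial upper limit under Risk of Agranulocytosis is computed on all clozapine-treated patients, so anyone admitted this way enters it. The one subgroup planned on ANC history (below 1500) would contain them without setting them apart. The planned regressions use mean pre-treatment ANC, which is not a record of past values below 500.

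**Working it through.** **1. The two rules side by side**

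| Past ANC record | Exclusion Criteria | Initiation item 1 |
|---|---|---|
| No value below 500 | may enter | may enter |
| One value below 500 | may enter | not enrolled |
| Two successive values below 500 | may enter | not enrolled |
| Three or more values below 500, never three in a row | may enter | not enrolled |
| Three or more successive values below 500 | excluded | not enrolled |

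The rules are nested: everyone barred by the first is barred by the second. They differ in the three middle rows. Applying both gives item 1, and the run-of-three wording then does no work.

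**2. Does any other text settle it?**

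- The consultation clause before the table and the table header permit exceptions. Neither ranks the two rules.
- The condition for starting clozapine refers to eligibility criteria without saying which rule is meant.
- Initiation item 3 concerns the current baseline count, not history.
- The row for ANC below 500 covers falls on clozapine (interruption, hematology decision, possible rechallenge), not entry.

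No section gives an order of precedence.

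**3. Precision cost of the stricter rule**

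The section on Risk of Agranulocytosis gives, for zero cases, 0.05 = (1 − r)^n. The one-sided 95% upper limit is therefore r = 1 − 0.05^(1/n).

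The plan's own figure: n = 212 gives 1 − 0.05^(1/212) = 1.403%, matching the stated 1.4%.

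The protocol does not say how many candidates have a past ANC below 500. The counts removed below are assumptions, taken out of the 212 and not replaced.

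| Removed (assumed) | Share of 212 | n left | Upper limit, zero cases | Change (points) |
|---|---|---|---|---|
| 0 | 0% | 212 | 1.403% | – |
| 1 | 0.5% | 211 | 1.410% | 0.007 |
| 5 | 2.4% | 207 | 1.437% | 0.034 |
| 10 | 4.7% | 202 | 1.472% | 0.069 |
| 20 | 9.4% | 192 | 1.548% | 0.145 |

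This prices the remedy only. It does not measure any effect of the inconsistency on Aim 3.

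**The case against.** The best reply is that item 1 is a gate on starting clozapine, laid over a broader entry list. It sits in the initiation row and opens by describing patients who start the drug. On that reading the run-of-three rule keeps people out of the whole study, including the observation and genotyping of Aims 1 and 2, while item 1 only withholds clozapine. The wording defeats this: item 1 says who is *enrolled*. Its other half, an ANC below 2500 in the past 24 months, also appears in STUDY DESIGN AND METHODS as a description of the enrolled cohort.

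Other parts of the reply stand. The rules are nested, so a site that reads both has a safe course. Departures from the table are provided for, with consultation. Previous counts are documented at Visit 1, so item 1 can be applied where records exist.

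Three stronger readings may tempt a reader, and the documents do not support them:

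- *FDA approved item 1 as an enrollment rule that overrides the exclusion list.* The stated approval is of the modified monitoring procedures, and the table is headed as a recommendation.
- *Item 2 sends these patients to clozapine on weekly draws with no hematology input.* Item 2 follows item 1 in the same cell, so this happens only if a site does not apply item 1.
- *The plan admits to leniency here.* The remark "We recognize that these are more lenient criteria than REMS" is attached to counts of 500-999 with hematology involvement. It says nothing about past values below 500.

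**Conclusion.** The inconsistency is real and concerns a safety eligibility criterion. The exclusion list and initiation item 1 differ for patients with one, two or non-successive past ANCs below 500, and the protocol does not say which governs. The risk is confined to a site that screens from the exclusion list alone.

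The number of patients affected is unknown. RISKS AND DISCOMFORTS does not expect on-study counts below 700, which suggests few such patients but does not count past values. A reader might infer that the Aim 3 estimate is biased. Nothing in the documents shows that: there is no count and no risk figure for these patients. If they did carry a higher risk, which is an assumption, including them would tend to raise the estimate and so would not flatter the safety claim. The only computable quantity is the cost of the stricter rule, at most 0.15 percentage points on the zero-case limit for up to 20 unreplaced losses.

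**What to change.** Amend the Exclusion Criteria so that any documented past ANC below 500 excludes, with an exception only after consultation of a physician, a hematologist and the PI as the Monitoring Guidelines provide. If hematology and FDA accept isolated past values, amend initiation item 1 to match the exclusion list instead; the existing provision for rechallenge after a fall below 500 on treatment would be in line with that choice. Either way, send the sites one rule.

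For any patient already treated who has a documented past ANC below 500, report the Aim 3 risk and upper limit with and without them, and state how many patients had no prior records to check.

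The cost is a one-line amendment, a site notice and one sensitivity analysis. Under the stricter rule a few candidates may lose eligibility. Replacement looks feasible: the site ranges in STUDY DESIGN AND METHODS run up to 90 + 150 + 50 = 290, against a target of 80 + 130 + 40 = 250. The with-and-without analysis may involve no patients at all. It is also limited by the records, because the section on Other Laboratory and Metabolic Monitoring collects existing values only where possible and with permission.

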Vital Signs (heart rate, BP, temperature, and respiratory rate)	X	X (weekly)	X	X (weekly) (Twice during week 7 and then weekly)
BMI assessment	X		X	X (monthly) Visits 10,14,18,22,26,30)
EKG (USA only)	X		X	
BPRS, CGI, CDS (when possible 2 x pre clozapine start)		X	X	X (monthly) Visits 10,14,18,22,26,30)
Pregnancy test (Females)	X		X	X (monthly) Visits 10,14,18,22,26,30)
Side Effect Checklist	X		X (2 x this week)	X (weekly)
Questionnaire on clozapine blood draw preferences			X (or earlier)	X (week 2 and 4)
SAS, BAS, AIMS	X		X	X (monthly) Visits 10,14,18,22,26,30)
Clozapine Serum Level (venous and capillary) ***				X (2x for first month, monthly thereafter)
Retrospective Chart review				X

*this will change according to participant and monitoring parameters if ANC <1200 cells/mm³

** WBC/ANC capillary lab results (3 part differential) will be drawn each week and will superscede full CBC (5 part differential) after 4 weeks in some instances. CBC can also be drawn when PI or physician request. Weekly monitoring of either venous or capillary will be required weekly throughout the study.

*** capillary blood draw for clozapine level is optional at the MPRC site and performed three times, once at baseline, once at approximately week 4 and once at approximately week 8. This is a prick of the finger with maximum of 3 ml for each stick. This is separate from fingerstick for ANCs that are only a few drops of blood

LABORATORY MONITORING:

White Blood Cell (WBC) and Absolute Neutrophil Counts (ANC):

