- All WBC with 3 to 5 part differential (by capillary and/or venous, respectively) will be obtained at the same time at each drawing when possible (approximately 9am to 12 pm) to avoid the confound of morning pseudoneutropenia and will be performed weekly for 6 weeks prior to clozapine and 6 months after clozapine. In participants who discontinue clozapine during the trial, weekly WBC/ANC measurements will be performed for an additional 4 weeks. The WBC and ANC at the two US sites will be performed by Lab Corp, which is fully licensed by the State of Maryland. The Laboratories Unit of the Maryland Department of Health and Mental Hygiene licenses laboratories and is responsible for ensuring federal certification of all laboratories located in Maryland, including federal certification in the Clinical Laboratory Improvement Amendments of 1988 Program, required for all clinical laboratory testing sites used in analysis of samples from US patients. WBC and ANC counts are calculated by automated cell counter by Lab Corp or by using The Athelas One lab using the Automated Haematology Analyzer .
- WBC and ANC at the Nigeria site will be performed in the well-equipped FNPHY Medical Laboratory using the Beckman Coulter (3 to 5 part differential) for automated counts with use of a microscope for manual WBC backup, under the direct oversight of [name], Head Medical Lab Technician. This laboratory routinely performs CBCs, is registered by the Medical Laboratory Sciences Council of Nigeria, the body for registration of diagnostic labs in Nigeria, and will abide by all requirements that are indicated when analyzing samples from Nigerian patients.
- WBC and ANC cutoff and reference criteria used for safety monitoring for clozapine are standardized in this protocol, so using different laboratories for these measurements are not of concern.
- If morning neutropenia occurs the afternoon (12-4pm) draw time is acceptable. The draw time will be documented.

Clozapine Blood Levels:

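### ANC may move from venous to finger-stick measurement after week 4 on clozapine, and the analysis cannot separate that change from a drug effect; common cut-offs do not make laboratories comparable either

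*Combined protocol and SAP*

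**What the plan says.** **Specimen.** In the Schedule of Events, a venous CBC with differential is planned at every pre-clozapine visit. On clozapine it is listed as "X (visit 7-10 and 30"). The finger stick first appears at visit 6 and is then "X (weekly) until week 4 then optional thereafter". A footnote adds that the capillary three-part result "will superscede full CBC (5 part differential) after 4 weeks in some instances", and another sentence reads "Weekly monitoring of either venous or capillary will be required weekly throughout the study". Both specimens are thus scheduled at visits 6-10, and no venous CBC is scheduled at visits 11-29.

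**Laboratories.** Under Laboratory Monitoring, US counts are obtained "by automated cell counter by Lab Corp or by using The Athelas One lab". The Nigerian site uses its own Beckman Coulter analyser with manual microscopy as backup. The same section says of its safety cut-offs and reference criteria that they are "standardized in this protocol, so using different laboratories for these measurements are not of concern".

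**Analysis.** Statistical Analyses states: "We will estimate the change from baseline in overall average WBC and ANC during each three month interval" after clozapine starts. It then tests for change over time with a repeated-measures mixed model adjusted for baseline. It also reports within-patient SDs and the frequency of values under 500, 700 and 1000. It names no specimen, analyser, laboratory or site term. Primary Outcome Variables lists ANC levels among the primary outcomes.

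**The concern.** Agreeing on a cut-off standardises the decision taken on a value. It does not show that two methods return the same value for the same blood. Here the method can change at a fixed point in treatment, about four weeks after clozapine starts, so a systematic difference between finger-stick and venous ANC is lined up with time on drug. The model would attribute it to clozapine. A negative offset would look like a fall in ANC, and a positive one could hide a real fall. A difference in precision alone would alter the within-patient SDs, which Aims 1 and 3 use to describe fluctuation.

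The plan accepts this logic elsewhere. It standardises draw time because of a possible confound. Under Clozapine Blood Levels it gives same-laboratory testing as a standardisation measure and plans paired capillary and venous drug levels to check that they match. No such check is specified for ANC.

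**Working it through.** **The plan's own figures.** The plan gives no SD, effect size or power for the ANC-change or genotype analyses, so there is nothing to reproduce for them. Its main precision figure concerns agranulocytosis: 250 × 0.85 = 212.5, taken as 212, and 1 − 0.05^(1/212) = 0.0140, which agrees with the stated 1.4%. That arithmetic is not affected by this point.

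**1. Share of capillary values per interval** (from the Schedule of Events). Treatment visits 7-30 are 24 weekly visits: 7-18 for months 1-3 and 19-30 for months 4-6. Assume that baseline is all venous, that a switcher uses finger stick after visit 10, and that the venous value is analysed at visits 7-10 and 30.
- Months 1-3: visits 11-18 are capillary, 8/12 = 0.67.
- Months 4-6: visits 19-29 are capillary, 11/12 = 0.92.

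**2. Bias.** Spurious change = f × share × b, where b is capillary minus venous and f the fraction switching. The false time trend is (0.92 − 0.67)fb = 0.25fb. In cells/mm³, with b assumed:

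| b | months 1-3, f = 1 | months 4-6, f = 1 | trend, f = 1 | months 1-3, f = 0.5 | months 4-6, f = 0.5 |
|---|---|---|---|---|---|
| 50 | 33 | 46 | 12.5 | 17 | 23 |
| 100 | 67 | 92 | 25 | 33 | 46 |
| 200 | 133 | 183 | 50 | 67 | 92 |

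The missing rule for duplicate values also matters. If capillary is used at visit 30 too, the months 4-6 share is 12/12 and the trend is 0.33fb. If capillary is used at every treatment visit, both shares are 1 and the trend vanishes, but the change from baseline is the full fb.

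**3. Effect on a test.** Take n = 212 and an assumed SD of patient-level change of 600, so SE = 600/√212 = 41.2. With f = 1, the chance that a two-sided 5% test declares a months 4-6 change when there is none is 20%, 60% and 99% for b = 50, 100 and 200. For b = 100 it is 92% at SD 400 and 39% at SD 800. At SD 600 with f = 0.5 and b = 100 it is 20%.

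**4. Threshold counts.** For an assumed patient mean of 1500 and within-patient SD of 400, the chance that a weekly value is below 1000 is Φ(−1.25) = 10.6%. An offset of −100 makes it Φ(−1.00) = 15.9%; +100 makes it Φ(−1.50) = 6.7%.

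**5. Laboratory offset L between sites.**
- Within-patient change, participant staying on one analyser: (value + L) − (baseline + L), so the bias is 0.
- DARC contrast: Study Design targets about 130 of 250 participants in Nigeria, and Subject Recruitment describes that population as pure for DARC. In the extreme case that all 130 are among the 212 null homozygotes and no non-null participant is Nigerian, the bias is 130/212 × L = 0.61L, or 31, 61 and 123 cells/mm³ for assumed L of 50, 100 and 200.

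**The case against.** The strongest reply is that the switch may be small. It is optional and happens only in some instances, and a physician may request a CBC at any time. The finger-stick device is named only under the US sites. The schedule does not restrict it to them, but if it were US-only, f could not exceed (80 + 40)/250 = 0.48, and the ceilings would be 0.32b and 0.44b: 64 and 88 cells/mm³ at b = 200. Laboratory Monitoring can also be read as allowing capillary counts before clozapine, which would shrink the bias. All of this stands as a limit on size. It does not remove the problem, because the plan neither fixes f nor measures b. Switching by choice may also be selective: the CBC schedule changes when ANC is below 1200, so specimen type may depend on ANC itself.

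A second reply is that low values are redrawn. The monitoring table does require an immediate redraw below 1000 and below 500. This protects the threshold counts in part, but the specimen for the redraw is not stated.

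A reader might also infer more than the documents support:
- That the plan dismisses the finger-stick switch. Its reassurance covers different laboratories only; on finger-stick versus venous ANC it is silent.
- That a site comparison is compromised. None is planned; the between-group contrast is by DARC genotype.
- That any laboratory difference contaminates the clozapine effect. A constant one cancels, unless a participant changes analyser or specimen type.

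**Conclusion.** The point holds for the specimen switch and, more narrowly, for laboratories. Any capillary-venous offset enters the estimated change in ANC as 0.67fb and then 0.92fb, with a false trend of 0.25fb, and it moves the threshold counts. Nothing in the planned analysis detects or removes it. These multipliers rest on an all-venous baseline, switching after visit 10, and venous values being analysed at visits 7-10 and 30. The size and sign of b, the fraction f, the SDs and L are not in the documents. The cell counts and error rates above are therefore ranges under assumption, not estimates of actual bias, and they do not show that an offset exists.

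The laboratory reassurance is sound for applying the safety cut-offs and unsound as a statement about measured values. What is exposed there is pooled ANC levels, threshold frequencies and the genotype contrast. The 1.4% limit is arithmetically unchanged, although finding cases below 500 depends on the assay. This should be corrected, because ANC level is a named primary outcome and the correction is cheap.

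**What to change.** 1. Limit the Laboratory Monitoring statement to application of the safety cut-offs.
2. Record specimen type and analyser for every ANC and WBC value.
3. Pre-specify which value is analysed when both specimens exist.
4. Estimate capillary-venous agreement (mean difference and spread) from the paired draws already scheduled at visits 6-10.
5. Add a specimen or method term to the ANC mixed model.
6. Add a site or laboratory term to between-participant comparisons, chiefly the DARC contrast. State that laboratory and site cannot be separated for Nigeria versus the US.
7. Report a venous-only sensitivity analysis on visits 1-10 and 30, plus any later venous CBC. State that for full switchers months 4-6 then rest on visit 30 alone, so it cannot reproduce the interval average.

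The cost is SAP wording, one extra data field or two, modest analysis work and slightly wider intervals. No new blood draws are needed. The pairs come from around the start of treatment, so using them later assumes that the offset stays constant; the report should say so.
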